Baseline evaluation visit

After confirmation of eligibility criteria, subjects will subsequently be randomized to one of the two treatment arms. They will then undergo MDS-UPDRS OFF and ON testing and Neuropsychological testing (ON). The practically defined OFF condition will be considered an overnight withdrawal of dopaminergic medications for 12 hours while ON evaluation will be performed 1 hour (\pm 15 minutes) after the administration of the usual morning dose of dopaminergic medications. The first daily dose of 0.6 mg and/or placebo, including injection instructions, will be administered at the end of the baseline visit. The baseline visit is to be conducted within 30 days of screening.

Commence treatment: 2-week titration

The following two visits will be dedicated to medication titration, up to 1.2mg (Week 1) and 1.8 mg (Week 2), as tolerated. At every visit, study drug compliance will be reviewed. Adverse events will be assessed and concomitant medications, routine vitals, and ECG, and blood and urine tests will be collected. A phone interview will be conducted following titration to determine which dosage (1.2 mg or 1.8 mg) the patient will remain on for the duration of the study.

Follow-up visit 1 and 2

4 and 12 weeks after titration is completed, a follow-up visit will establish whether the subjects are tolerating study medications, including an assessment of adverse events, concomitant medications, routine vitals, an ECG, and blood and urine tests.

Follow-up visit 3 (6 month)

26 weeks after completing titration, subjects will undergo repeat MDS-UPDRS OFF and ON testing and

Neuropsychological testing (ON) in addition to an assessment of adverse events, concomitant medications, routine vitals, an ECG, and blood and urine tests.

Follow-up visit 4 (9 months)

36 weeks after titration is completed, a follow-up visit will establish whether the subjects are tolerating study medications, including an assessment of adverse events, concomitant medications, routine vitals, and ECG, and blood and urine tests.

End visit

52 weeks after completing titration, subjects in both treatment arms will undergo an exit visit including MDS-UPDRS OFF and ON testing and neuropsychological testing (ON) in addition to an assessment of adverse events, concomitant medications, routine vitals, an ECG, and blood and urine tests. At this stage, study treatment will be discontinued.

Post-study visit

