4 weeks after the end of the study, a phone interview will be completed to assess adverse events which were ongoing at the end visit (Week 54) and concomitant medications.

Post-study follow-up (6 month)

26 weeks after completing the active phase of the study (end visit), subjects originally assigned to both treatment arms will undergo a follow-up visit including MDS-UPDRS OFF and ON testing and neuropsychological testing (ON) in addition to an assessment of adverse events which were ongoing at the end visit (Week 54), concomitant medications, routine vitals, an ECG, and blood and urine tests. At this stage, enrolled subjects will no longer be on study treatment. However, the study team may continue to follow subjects who opt to continue liraglutide off-label.

Post-study follow up (12 month)

52 weeks after completing the active phase of the study (end visit), subjects originally assigned to both treatment arms will undergo a follow-up visit including MDS-UPDRS OFF and ON testing and neuropsychological testing (ON) in addition to an assessment of adverse events which were ongoing at the end visit (Week 54), concomitant medications, routine vitals, an ECG, and blood and urine tests. At this stage, enrolled subjects will no longer be on study treatment. However, the study team may continue to follow subjects who opt to continue liraglutide off-label.

STUDY DRUGS AND MATERIALS:

Study Medications: Liraglutide 6 mg/ml (Novo Nordisk A/S) will be self-administered subcutaneously once daily at a maximum dose of 1.8 mg after a 2 week titration schedule. Placebo will be administered according to the same schedule (Table 2). At baseline, subjects will be dispensed drug pens preset to deliver 0.6 mg of either liraglutide or vehicle per daily dose. At week 1 visit, after being assessed for tolerability by the investigator, subjects will be titrated to 1.2 mg of either liraglutide or vehicle per daily dose. The same procedure will be repeated at week 2, when subjects will be titrated to 1.8 mg of either liraglutide or vehicle per daily dose, as tolerated. A subject that cannot tolerate at least a 1.2 mg dose will be excluded from the study. Subjects that cannot tolerate the 1.8 mg dose, will be offered to continue at the 1.2 mg dose. The project will include a washout period at study end.

Table 2

Week	Titration Schedule	
	Drug Group	Placebo Group
	Liraglutide Dose	Vehicle Dose
Baseline	0.6 mg	0.6 mg
Week 1	1.2 mg	1.2 mg

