Collection, Recording, and Reporting of Adverse Events (AEs): The collection of non-serious AE data and serious adverse event (SAE) information commences following the subject's written consent to participate in the study. An AE is any untoward medical occurrence in a clinical investigation subject administered an investigational product and which does not necessarily have to have a causal relationship with this treatment. An AE can therefore be any unfavorable and unintended sign (including an abnormal laboratory finding, for example), symptom, or disease temporally associated with the use of a medicinal product, whether or not considered related to the medicinal product (study drug). An Adverse Reaction (AR) is an AE for which a causal relationship to the trial product is at least possible, i.e. a causal relationship is conceivable and cannot be dismissed.

The description of each AE will identify the subject, date of onset, the date of resolution, the severity of the event, the action taken regarding study drug, the outcome of the event, and the relationship of the event to study drug. AE information will be entered in the CRF within 7 days of the information becoming available in order to ensure timely reporting to the Sponsor.

Severity of reported AEs will be evaluated using the following guidelines:

- Mild: The subject is aware of the AE but it is easily tolerated.
- Moderate: The AE causes the subject discomfort and interrupts the subject's activities of daily life.

- Severe: The AE is debilitating or results in the inability of the subject to perform the activities of daily life.

The Investigator will use the following definitions to evaluate the relationship of each AE to the study drug:

Definitely: An AE that follows a reasonable temporal sequence from administration of the study drug (including the course after withdrawal of the study drug) and that satisfies any of the following:

- reappearance of a similar reaction upon re-administration (positive rechallenge);
- toxic level of the study drug as evidenced by measurement of study drug concentrations in blood or other bodily fluid.

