- An important medical event: Those events that may not be immediately life-threatening or result in death or hospitalization but based upon appropriate medical and scientific judgment may jeopardize the subject or may require intervention to prevent one of the serious outcomes listed above.
- Suspicion of transmission of infectious agents must always be considered an SAE.

A Serious adverse reaction (SAR) is an adverse event that fulfils both the criteria for a Serious Adverse Event and the criteria for an Adverse Reaction.

A Suspected Unexpected Serious Adverse Reaction (SUSAR) is a SAE that is unexpected and regarded as possibly or probably related to the trial/study product by the investigator.

SAEs require expeditious handling to comply with regulatory requirements. Any SAE, SAR or SUSAR occurring in a clinical study subject will be reported to the Institutional Review Board (IRB) within 10 days of the Investigator having knowledge of the SAE. In addition, the investigator will copy Novo Nordisk A/S (NN) when expediting SARs or SUSARs to health authorities and will report all SARs related to NN Product to the local NN affiliate safety department. The submission to NN will be within day 15 from the investigator's first knowledge about a valid case. The Investigator or other qualified individual at the investigative site will complete an SAE form including study name, name of the reporter, subject identification (e.g. subject number, initials, gender, age), event (preferably diagnosis), study drug, most recent date of administration, the Investigator's causality assessment to study drug (as outlined above) and outcome.

Follow-up of Adverse Events: If a subject experiences an SAE or AE, the subject will receive appropriate treatment and supportive care, as necessary, and the PI will continue to follow-up until there is a return to the subject's baseline condition, or until a clinically satisfactory resolution is achieved.

Pregnancy Beginning During Course of Trial: Female study subjects will be advised by the Investigator to inform him immediately if she suspects she may be pregnant up to 30 days after the last dose of study drug.

Male study subjects will be advised by the Investigator to inform him immediately if he suspects his partner became pregnant up to 30 days after the last dose of study drug.

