PREMATURE TERMINATION OF STUDY: In case the study is terminated early due to the discovery of an unexpected, significant, or unacceptable risk/safety concern, regardless of how far along the subject has reached in their study follow-up, subjects will be asked to return all unutilized pens to the PI. The study site will then return investigational drug to the drug manufacturer (See also Study Drug Accountability).

PUBLICATION PLANS: The intention of the study will be to publish the results of the complete study at conclusion. All information obtained during the conduct of this study will be regarded as confidential but no written permission from the study funding sources is required prior to disclosing any information relative to this study. A formal publication of data collected as a result of the study will be considered a joint publication by all investigators and appropriate personnel. Authorship will be determined by mutual agreement. Submission to the funding source(s) for review and comment will be intended solely to ensure concurrence regarding data, evaluations, and conclusions, and to provide an opportunity to share with them any new or unpublished information of which they may be unaware.

Schedule of events

Procedures	Screening	Baseline	Week 1	Week 2	Week 3	Week 6	Week 14	Week 28	Week 40	Week 54	Week 58	Week 80	Week 108
Day	Within 30 days of baseline	1	8 + 3	(7+3 days from Week 1)	(7+3 days from Week 2)	42 ± 7	98 ± 7	196 ± 7	280 ± 7	378 ± 7	406 ± 7	560 ± 7	756 ± 7
Sign Consent	x												
Demographics	x												
Medical History	x												
Pregnancy Test	x												
Physical and Neuro Exam	x												
EKG	x		x	x		x	x	x	x	x		x	x
Vitals	x	x	x	x		x	x	x	x	x		x	x
Blood and Urine samples¹	x		x	x		x	x	x	x	x		x	x
Blood for Biomarker Analysis	x							x		x		x	x
Review of eligibility		x											
MDS-UPDRS OFF²		x						x		x		x	x
MDS-UPDRS ON		x						x		x		x	x
BDI-II	x												
NMSS		x						x		x		x	x
MDRS-2	x							x		x		x	x
Neuropsych tests		x						x		x		x	x
Treatment Randomization and First Dose		X (0.6) Placebo	X (1.2) Placebo	X (1.8) Placebo									
Drug Administration Training		x	x	x									
Dispense Study Drug		x	x	x		x	x	x	x				

Review Study Drug Compliance			X	X		X	X	X	X	X			
AE Assessment	X	X	X	X	X	X	X	X	X	X	X	X	X
Assessment of Concomitant Medications		X	X	X	X	X	X	X	X	X	X	X	X
Final dosage determination³					X								

1) Lab tests – schedule across study:

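### The post-study visit text limits adverse event assessment to events ongoing at Week 54, which conflicts with the schedule table and the adverse event sections; no end of collection is defined

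*Combined protocol and SAP*

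**What the plan says.** Study drug stops at the Week 54 end visit: "At this stage, study treatment will be discontinued". Three contacts follow.

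- **Week 58 call** (Study Schedule, Post-study visit): "a phone interview will be completed to assess adverse events which were ongoing at the end visit (Week 54) and concomitant medications".
- **6-month and 12-month post-study visits** (same section): each includes "an assessment of adverse events which were ongoing at the end visit (Week 54), concomitant medications, routine vitals, an ECG", together with blood and urine tests.

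At Follow-up visits 1 and 2, during treatment, the wording has no such limit: "including an assessment of adverse events, concomitant medications, routine vitals, an ECG, and blood and urine tests". The 6-month, 9-month and end visits on treatment are likewise unrestricted.

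The Schedule of events has a row "AE Assessment" marked at every visit, including Weeks 58, 80 and 108, with no footnote narrowing it. The section on collection, recording and reporting of AEs starts collection at consent, gives no end date, and counts a laboratory abnormality as a possible AE.

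**The concern.** The restriction appears exactly where treatment stops. Read literally, an event that begins the day after the last dose is not asked about at the Week 58 call or at either later visit. Safety is part of the primary objective, and adverse events come first in the list of safety outcomes.

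Two things are at stake. If the visit text is followed, a low count of new post-treatment AEs would partly reflect the question asked. If some staff follow the text and others the table, the count mixes two rules and cannot be interpreted in either arm. The protocol also allows follow-up of participants who continue liraglutide off-label after Week 54, so some events in this period may arise under continued exposure. The post-study text makes no separate provision for them.

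**Working it through.** No power or sample-size arithmetic applies. The check compares the places that govern AE collection after the last dose, then works out the length of the period.

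**What each place asks for after Week 54**

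| Place | Scope for new-onset events |
|---|---|
| Study Schedule, Week 58 call | Ongoing events only |
| Study Schedule, 6- and 12-month post-study visits | Ongoing events only, though ECG, vitals and laboratory tests are repeated |
| Schedule of events, AE row | Marked at Weeks 58, 80 and 108, unrestricted |
| Precautions/Over-dosage | Participants asked about any adverse effect as it arises and at every scheduled visit |
| Collection, Recording, and Reporting of AEs | From consent, no end date; laboratory abnormalities can be AEs |
| SAE reporting (same section) | Any SAE in a participant, no cut-off after the last dose |
| Laboratory footnote to the schedule | CBC, CMP, amylase, lipase, calcitonin and urinalysis at Weeks 80 and 108 |
| List of safety outcomes | Laboratory parameters and ECGs listed separately from AEs |

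The first two rows cannot be reconciled with the next four, and nothing says which governs.

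**Consequence by type of event, if the visit text is followed**

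1. *New non-serious AE.* Not asked about at any of the three contacts. It reaches the database only if the participant volunteers it or staff apply the table.
2. *New SAE.* Reportable whenever it occurs. The 10-day clock for reporting to the IRB starts when the investigator learns of it, however, and the scheduled contacts are not told to ask.
3. *New laboratory or ECG abnormality at Week 80 or 108.* The value is collected and belongs to a listed safety outcome. Whether it is also recorded as an AE, with severity and causality, is not stated.

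**Length of the period**, from the days in the Schedule of events (Week 54 = Day 378):

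- Week 58: (406 − 378)/7 = 4 weeks, as in the text.
- Week 80: (560 − 378)/7 = 26 weeks, as in the text.
- Week 108: (756 − 378)/7 = 54 weeks. The text puts this visit 52 weeks after the end visit, which is Week 106, or Day 106 × 7 = 742. That lies outside the table's window of 756 ± 7, i.e. Days 749 to 763.

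The period is therefore 54 weeks by the table and 52 by the text, about as long as the treatment period. The two-week difference is a separate discrepancy and does not change this point.

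**The case against.** The strongest reply is that the visit text is not the only instruction. The AE row is unrestricted, the Precautions/Over-dosage section has participants asked about any adverse effect at each scheduled visit, collection has no end date, and any SAE must be reported. A reader might infer from the post-study paragraphs alone that events beginning after Week 54 are not captured at all, or that their count is zero by construction. The documents do not support that: it treats the narrowest of several conflicting instructions as the only one. Nor do they support saying that late laboratory or ECG signals would be missed, because those data are collected at Weeks 80 and 108 and are safety outcomes in their own right.

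Two supporting passages also carry less weight than they seem to. The causality definitions refer to the time course after an event, "including the course after withdrawal of the study drug", but they grade relatedness and set no collection window. The pregnancy rule, under which a female participant should "inform him immediately if she suspects she may be pregnant up to 30 days after the last dose of study drug", is a separate procedure. It shows that at least one kind of new post-dose event is collected.

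Finally, how far to collect non-serious AEs 6 to 12 months after the last dose is a judgement on which statisticians may differ.

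All of this stands, and it limits the point to a conflict that must be resolved. It does not remove the conflict. The wider passages do not override the explicit limit, which is stated three times, and the judgement about Weeks 80 and 108 does not explain the same limit at the call 4 weeks after the last dose.

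**Conclusion.** The point holds as an internal conflict. The post-study text is narrower than the schedule table, the AE collection section, the Precautions/Over-dosage section and the SAE reporting rule, and no end of AE collection is defined. The conflict itself is certain from the wording. Its effect depends on which instruction staff follow. It falls mainly on new non-serious AEs, and on whether new laboratory or ECG abnormalities at Weeks 80 and 108 become AE records.

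It touches all three post-treatment contacts, over 54 weeks (table) or 52 weeks (text). No number of affected events can be given, because the documents contain no rate for onset after stopping. The change should be made: safety is part of the primary objective, and the contacts already exist.

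**What to change.** 1. Delete the restriction from the Week 58 paragraph, so that the call records AEs with onset since Week 54 as well as those still open.
2. For Weeks 80 and 108, reconcile the visit text with the AE row, the AE collection section, the Precautions/Over-dosage section and the SAE rule. The agreed wording should record at least new SAEs and clinically relevant new laboratory or ECG abnormalities. Whether to collect all new non-serious AEs at these visits is for the team to decide, but the rule should be explicit and the same for both arms.
3. State when AE collection ends.
4. In the analysis, tabulate events with post-treatment onset separately from on-treatment events, and flag participants taking liraglutide off-label after Week 54.

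The cost is a wording change, a few more CRF entries at contacts already planned, and some unrelated background events, which the separate table keeps apart. No visit, test or treatment rule changes.
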